## 4.4 Treatment Group

Treatment was performed at the physician's discretion. The subjects included in this retrospective study were treated with Turbo Power laser atherectomy as well as drug-coated balloon angioplasty.

## 5. SAMPLE SIZE AND STATISTICAL CONSIDERATIONS

**5.1** The study is designed to include up to 120 patients. Descriptive statistics (arithmetic mean, median as indicated, minimum and maximum and standard deviation) will be calculated for continuous variables. Absolute frequencies and percentages will be obtained for qualitative variables. 95% Confidence intervals will be provided. In

calculation of percentages, patients with missing data will not be considered, unless otherwise specified. All baseline characteristics will be summarized. Descriptive statistics will be used to summarize the values and changes from baseline across time.

## **6. PROCEDURES**

### **6.1 Data Review**

All patients from Cardiovascular Institute of the South who were treated for femoropopliteal de novo/restenotic lesions or in-stent restenosis using Turbo Power laser atherectomy plus drug coated balloon angioplasty between 2016-2017 will be considered for study enrollment.

A review of the study candidate's medical history, procedure and data 12-months post-procedure will be performed and documented on the study CRFs.

Up to 20 patients that have been compliant with the physician's discharge instructions will be included in a subgroup. This subgroup will be specifically reviewed for long-term patency by the duplex ultrasound core lab. These patients will have a duplex ultrasound conducted within 305-425 days post-procedure ( $\pm 60$  days of 12-months post-procedure).

### **6.2 Angiographic Core Lab**

An angiographic core lab will be employed to review procedural angiography on the 120 patients. They will assess baseline lesion characteristics and post-procedural diameter stenosis.

### **6.3 Duplex Ultrasound Core Lab**

In the 20 patient subgroup, restenosis of the target lesion will be assessed by the duplex ultrasound core lab. These patients will have a duplex ultrasound conducted within 305-425 days post-procedure ( $\pm 60$  days of 12-months post-procedure). This will provide long-term patency data in these 20 patients.

## **7. ETHICAL PROCEDURES**

### **7.1 Declaration of Helsinki**

This study will be conducted according to the US FDA standards of Good Clinical Practice (FDA Title 21 Code of Federal Regulations part 11, 50, 54, 56 and 812), the Declaration of Helsinki, and the ICH Guidelines.

### **7.2 Patient informed consent**

We are requesting a waiver of consent from IRB as this is a retrospective review and the data already exists. The patient's personal identifying information will not be compromised or disclosed.

Data from patients that have previously declined consent will not be included in the study.

### **7.3 Institutional Review Board (IRB)**

The study may not be started at the proposed medical institution until all required approvals for the study have been obtained.

## **7.4 Deviations from the Investigational Plan**

An Investigator is required to conduct this study in accordance with this investigational protocol, applicable laws and regulations, and any conditions of approval imposed by the Ethics Committees.

- An Investigator shall notify the reviewing Ethics Committee of any deviation from the investigational plan to protect the life or physical well being of a patient in an emergency. Such notices shall be given as soon as possible, but no later than 3 working days after the emergency has occurred.
- Except in such an emergency, prior approval by the Ethics Committee is required for a change in or deviation from the plan that could affect the scientific soundness of the plan, or the rights, safety or welfare of the patients.

## **8. DATA COLLECTION AND MANAGEMENT**

### **8.1 *Required Data***

For the duration of the study, the Investigator and their delegates will maintain complete and accurate documentation, including but not limited to, medical records, study progress notes, signed subject informed consent forms (if applicable), correspondence with the reviewing IRB, correspondence with the Sponsor's designee and Study Monitor, adverse event reports, and information regarding subject discontinuation or completion of the study.

### **8.2 *Missing Values and Sensitivity Analysis***

Every attempt will be made to obtain missing values. Missing values will be queried and reconciled where possible. In the event missing values are unable to be resolved, sensitivity analyses will be conducted and compared using various scenarios.

### **8.3 *Confidentiality***

Information about study subjects will be kept confidential and managed according to the requirements of the Health Insurance Portability and Accountability Act of 1996 (HIPAA). Those regulations require a signed subject authorization informing the subject of the following:

- What protected health information (PHI) will be collected from subjects in this study
- Who will have access to that information
- Who will use or disclose that information
- The rights of a research subject to revoke their authorization for use of their PHI.

In the event that a subject revokes authorization to collect or use PHI, the investigator, by regulation, retains the ability to use all information collected prior to the revocation of

subject authorization. For subjects that have revoked authorization to collect or use PHI, attempts should be made to obtain permission to collect at least vital status (i.e. that the subject is alive) at the end of their scheduled study period.

All data and information collected during this study will be considered confidential by the. All data used in the analysis and summary of this study will be anonymous, and without reference to specific subject names. Access to subject files will be limited to authorized personnel of the Investigator, Clinical Site research staff and authorized Regulatory Authorities. Authorized regulatory personnel have the right to inspect and copy all records pertinent to this study

#### **8.4 *Source Documents***

Source data is all information, original records of clinical findings, observations, or other activities in a clinical trial necessary for the reconstruction and evaluation of the trial. Examples of these original documents, and data records include but are not limited to: hospital records, clinical and office charts, laboratory notes, memoranda, subjects' diaries or evaluation checklists, recorded data from automated instruments, copies or transcriptions certified after verification as being accurate and complete, microfiches, photographic negatives, microfilm or magnetic media, x-rays, subject files, and records kept at the pharmacy, at the laboratories, and at core laboratories involved in the clinical trial.

Regulations require that the Investigator maintain information in the subject's medical records that corroborate data collected for the study.

#### **8.5 *Case Report Forms***

This study will use a paper case report form (CRF) as the primary data collection instrument and data will be entered into an electronic database at the sponsor site. All data requested on the CRF should be entered or if missing, explained. If any entry error has been made, correct and enter the correct data in the CRF.

#### **8.6 *Record Retention***

The Investigator will retain study essential documents for at least two years after completion of the trial.

### **9. Abbreviations/Definitions**

**Acute Procedural Success:** Defined as a  $\leq 30\%$  residual stenosis in the target lesion immediately post assigned treatment. This assessment will be correlated with the ACL finding.

**Claudication:** Poor circulation and blockage of blood in the leg arteries produces an aching, tired, cramping and sometimes burning pain in the hips, thighs, or calves when the leg muscles do not receive the oxygen rich blood required during exercise or at rest.

**Dissection:** A separation of the vessel structures or formation of a false lumen. Flow-limiting dissection is considered Grade D or greater.

**GRADE DISSECTION DESCRIPTION**

- A** Small radiolucent area within the lumen of the vessel disappearing with the passage of the contrast material.
- B** Filling defect parallel to the lumen of the vessel disappearing with the passage of contrast material.
- C** Dissection protruding outside the lumen of the vessel persisting after passage of contrast material.
- D** Spiral shaped filling defect with delayed runoff of the contrast material in the distal vessel.
- E** Persistent luminal filling defect with delayed anterograde flow
- F** Filling defect accompanied by total occlusion

**Distal Embolization:** Free-flowing blood clot or lesion material located distal from the treated lesion. Significant distal embolization: In event of clinical sequelae, treatment was needed to remove emboli.

**Major Amputation:** Unplanned amputation of the target limb where prosthesis is required for standing or walking.

**Occlusion:** No flow identified within the arterial segment by ultrasound and/or angiogram.

**Patency:** Loss of patency will be determined by duplex ultrasound (DUS). DUS analysis will be performed per core lab protocol

**Percent Stenosis:** Native vessel diameter as measured at the most narrow point of the lesion divided by the estimated native vessel diameter at that location using angiographic images with visual estimate.

**P1 Segment of the Popliteal Artery:** the first portion of the popliteal artery between the Hunter canal and the popliteal fossa.

**P2 Segment of the Popliteal Artery:** from the popliteal fossa to the knee joint

**P3 Segment of the Popliteal Artery:** from the knee joint to the take-off of the anterior tibial artery

**Provisional Procedures:** Additional devices used at time of procedure that exclude Turbo Power laser atherectomy and drug-coated balloon.

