## **3. DESIGN**

This is a retrospective, single-site, non-randomized study. Up to 120 subjects will be included in this study at Cardiovascular Institute of the South. Patient data will be reviewed through 12 months post-procedure. Out of the 120 patients, up to 20 patients will be included for a sub-analysis of patency. These 20 patients must be compliant with physician discharge instructions to be included in this cohort.

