### **Primary Endpoint:**

Rate of freedom from target lesion revascularization (TLR) at one year

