### **Secondary Endpoints:**

The secondary endpoints consist of:

- Procedural success ( $\leq 30\%$  residual stenosis)
- Procedural safety (freedom from significant embolization (sequelae), or dissection)
- Freedom from major amputation at 30d, 6mo & 12mo
- Freedom from death at 30d, 6mo & 12mo
- Freedom from TLR 6 months
- Patency at 12 months (up to 20 patients)

The device involved in this study is the Spectranetics' Turbo Power laser catheter followed by drug coated balloon angioplasty. These devices are currently available in the United States. The Turbo Power laser catheter is currently indicated for the treatment of peripheral arterial disease including treatment of in-stent restenosis (ISR). Additionally, the two drug-coated balloons on the market in the United States during this retrospective timeframe were IN.PACT Admiral (Medtronic) and Lutonix 035 (CR Bard). They are both indicated for treatment of peripheral arterial disease and specifically, IN.PACT Admiral is indicated for ISR treatment. The present protocol does not involve invasive investigational interventions.

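### As written, 12-month patency rests on duplex alone, so a lesion re-treated before the scan and open on it counts as patent

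*Combined protocol and SAP*

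**What the plan says.** Patency at 12 months is a listed secondary endpoint, limited to at most 20 of up to 120 patients. Section 9 (Patency entry) defines it in two sentences: "Loss of patency will be determined by duplex ultrasound (DUS). DUS analysis will be performed per core lab protocol". Section 6.3 gives the duplex core lab the task of assessing restenosis in the target lesion and sets the timing: "These patients will have a duplex ultrasound conducted within 305-425 days post-procedure". Section 6.1 gives the same window.

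TLR has its own entry in section 9, covering any repeat percutaneous or surgical treatment of a restenosed or reoccluded target lesion. It is a separate endpoint, and the primary one is "Rate of freedom from target lesion revascularization (TLR) at one year". No section connects TLR to patency, and none distinguishes patency with repeat treatment from patency without it. Section 3 limits chart review: "Patient data will be reviewed through 12 months post-procedure".

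On who enters the subgroup, section 3 says "These 20 patients must be compliant with physician discharge instructions to be included in this cohort", and section 6.1 says "Up to 20 patients that have been compliant with the physician's discharge instructions will be included in a subgroup". Compliance is not defined. No rule covers the case where more than 20 qualify, and nothing requires the choice to be made without knowledge of outcome.

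**The concern.** The stated objective is the outcome of laser atherectomy plus drug-coated balloon. If that treatment failed, the lesion was re-treated and the scan then shows an open vessel, the scan reflects the repeat procedure. A duplex-only rule records this as a success of the index treatment. Relative to a rule that also counts TLR, the misclassification runs in one direction, and a confidence interval does not allow for it.

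There is also a small timing gap. Scans may take place up to day 425 but charts are reviewed only through 12 months, so a TLR between day 365 and a late scan might not be recorded at all.

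A secondary matter is selection. The study is retrospective, compliance is undefined and there is no order of entry, so a reader of the result cannot tell how the patients were chosen.

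**Working it through.** The plan gives no expected patency rate, TLR rate or precision target for this endpoint, so there is no figure of that kind to reproduce. The one checkable figure is the scan window: 365 − 60 = 305 and 365 + 60 = 425, which agrees with sections 6.1 and 6.3.

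**1. What the text does with a re-treated lesion.** Take a patient with restenosis and TLR at month 7 and an open lesion on a scan at day 370.
- TLR endpoint (sections 3 and 9): failure.
- Patency (section 9): decided by duplex, which shows no restenosis, so patent.
- No other section overrides this. The section 9 entry on occlusion mentions ultrasound or angiogram but is not tied to patency.

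**2. Direction.** Lesions that are open on the scan and free of TLR are a subset of those open on the scan. In the same patients, the duplex-only figure can therefore equal or exceed the combined figure, never fall below it.

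**3. Size per patient** (one target lesion per patient assumed). At 20 patients: 1/20 = 5 points. Twenty is a maximum; at 10 patients: 1/10 = 10 points.

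**4. Illustration.** Suppose 16 of 20 are open on the scan, and k of those 16 had an earlier TLR. Exact (Clopper-Pearson) 95% intervals:

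| k | Combined patency | 95% CI |
|---|---|---|
| 0 | 16/20 = 80% | 56.3–94.3% |
| 1 | 15/20 = 75% | 50.9–91.3% |
| 2 | 14/20 = 70% | 45.7–88.1% |
| 3 | 13/20 = 65% | 40.8–84.6% |
| 4 | 12/20 = 60% | 36.1–80.9% |

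**5. How many might be affected.** The documents give no rates, so these are assumptions: a fraction q = 5% to 20% re-treated before the scan, and a fraction r = 50% to 90% of those open on it. The number affected is taken as Binomial(20, q×r).
- Low end: q×r = 0.05 × 0.5 = 0.025. Expected 20 × 0.025 = 0.5 patients (2.5 points). P(none) = 0.975^20 = 0.60. Central 95% range 0–2 patients (0–10 points).
- High end: q×r = 0.20 × 0.9 = 0.18. Expected 20 × 0.18 = 3.6 patients (18 points). P(none) = 0.82^20 = 0.02. Central 95% range 1–7 patients (5–35 points).

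**6. Chart-review gap.** The latest scan is day 425 and review ends at 12 months: 425 − 365 = 60 days in which a TLR might be missed.

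**The case against.** The strongest reply is that scoring is delegated to a core lab protocol that is not among the documents and may already treat TLR as loss. That is possible, and it is why the point is limited to the text as written. But the reference to that protocol covers the analysis of the ultrasound, and nothing says the duplex core lab receives TLR data.

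A second reply is that the protocol never promises patency free of repeat treatment, and that duplex patency beside a separate TLR endpoint is a recognisable choice. This stands in part: clear labelling would meet some of the concern. The present wording, however, does not tell a reader which quantity is being reported.

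A third reply is that the endpoint is small, descriptive and already called a sub-analysis, and that its interval at 16/20 spans 94.3 − 56.3 = 38 points. This stands and sets the severity.

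Three stronger readings are tempting and not supported:
- *That reported patency will be inflated.* The documents do not show that any of these patients was re-treated before the scan. At the low end of the assumed rates there is a 60% chance that none is affected.
- *That the subgroup was picked with outcomes in view, or that choosing compliant patients raises patency.* Section 7.2 notes that the data already exist, but it does so to support the consent waiver. Sections 6.1 and 6.3 speak of the scan as still to be done. Neither knowledge of outcome nor the size or direction of a selection effect can be derived.
- *That leaving out unscanned patients, as section 5.1 would ("patients with missing data will not be considered, unless otherwise specified"), while counting TLR as failure must over-count failures.* The direction depends on patency in the unscanned. Assume 20 patients, 3 with TLR, 17 without, 80% of the 17 scanned and 90% of those open. Then 13.6 are scanned, 12.24 are open and 3.4 are missing, and dropping the missing gives 12.24/16.6 = 73.7%. The full value is (12.24 + 3.4m)/20, where m is patency in the missing. It exceeds 73.7% only if m is above about 74%. With 60% or 40% scanned, the turning point is about 70% (9.18/13.2) or 62% (6.12/9.8).

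**Conclusion.** The point holds as a gap in the definition. Unless the unseen core lab protocol closes it, following section 9 scores a re-treated, open lesion as patent. Relative to a definition that counts TLR, the effect can only be upward: 5 points per affected patient at 20 patients, and more if fewer are included. The count is unknown and may be zero. The expected excess of 2.5 to 18 points rests wholly on assumed re-treatment and re-opening rates and on one lesion per patient, and should not be quoted as a finding about this study.

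The lack of a selection rule is a reporting gap and a reason for a safeguard; it does not demonstrate bias. The primary endpoint is unaffected. Severity: minor, and worth correcting because the remedy is cheap.

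**What to change.** 1. In the Patency entry of section 9, define 12-month patency as no core-lab duplex restenosis or occlusion on the in-window scan **and** no TLR of the target lesion up to the later of day 365 and the scan date. Report duplex-only patency alongside, labelled as such. For patients scanned after day 365, extend chart review to the scan date, and align the Protocol Summary (Duration), section 3 and section 6.1. Section 7.4 may require prior Ethics Committee approval.

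2. As a secondary safeguard, in sections 3 and 6.1 define compliance without reference to outcome. Take compliant patients with an in-window scan consecutively by index procedure date, up to 20, regardless of TLR status and without knowledge of the scan result. Report the numbers compliant, scanned and selected. State that the result describes compliant, scanned patients, and compare their baseline features and one-year TLR with the rest of the cohort.

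Cost: TLR is already collected for the primary endpoint, and core-lab readings stay at 20 or fewer. The extra work is up to 60 days of further review in at most 20 charts, some wording and possibly an ethics submission. The patency figure will probably be lower. TLR cut-offs will still vary between day 365 and day 425, and the subgroup remains conditional on having been scanned. Requiring a scan at entry is deliberate: admitting patients without one would create missing outcomes.

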## 1. BACKGROUND INFORMATION

Peripheral artery disease (PAD) is a condition where arteries become narrowed due to plaque and thrombus buildup and this reduces blood flow to the limbs. Millions of Americans are affected by PAD and many more may be asymptomatic. Individuals with PAD have an increased risk for heart disease, aortic aneurysms, stroke and an increased mortality. Due to the prevalence of PAD in society, research is ongoing to help treat this disease.

Percutaneous transluminal angioplasty (PTA) has been one of the most widely used methods of treating PAD; however, it is well known that complications and patency rates are disappointing. Many studies have suggested combining PTA with a debulking therapy could provide better results so there is less tissue compressed. There are many atherectomy devices on the market, but to our knowledge, there is a need to determine the optimal algorithm to best treat PAD.

Excimer laser ablation (ELA) has been performed since 1994 when the first devices received CE mark. There are many devices that modify or remove obstructions in the arteries, but the Excimer laser is unique as it ablates or vaporizes tissue at the catheter tip. The catheter contains optical fibers that transmit pulses of ultraviolet light at 308nm that break down blockages at the molecular level. The laser catheters ablate lesions consisting of plaque, thrombus, neointimal hyperplasia, and calcium.

The Laser Angioplasty for Critical Ischemia (LACI) Registry used excimer laser catheters ranging from 0.9 to 2.5 mm to debulk infrainguinal arteries followed by balloon angioplasty and optional stenting. From visual assessment, baseline lesion stenosis was  $92\% \pm 12\%$  and after laser use, this decreased to  $55\% \pm 24\%$  ( $p < 0.001$ ). 88% of lesions were located in the femoropopliteal arteries.

The CELLO Registry used excimer laser catheters to enlarge the lumen of the superficial femoral artery or proximal popliteal. A 2.0mm Turbo-Elite laser catheter was used to create a pilot channel and the Turbo Booster laser catheter was utilized to increase the lumen diameter. The primary effectiveness endpoint for this study was a decrease of 20% or greater after all laser by core lab assessment. During the study the diameter stenosis was reduced from  $77\% \pm 15\%$  at baseline to  $34.7\% \pm 17.8\%$  post all laser.

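### Percent stenosis is defined as the share of the vessel left open, so the ≤30% procedural-success rule is reversed as written

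*Combined protocol and SAP*

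**What the plan says.** The Percent Stenosis entry in section 9 (Abbreviations/Definitions) of the combined protocol and SAP reads "Native vessel diameter as measured at the most narrow point of the lesion divided by the estimated native vessel diameter at that location", and continues "using angiographic images with visual estimate". The sentence is complete, with no subtraction in it and no sign of missing text.

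The quantity feeds an endpoint. Procedural success, at 30% or less residual stenosis, heads the list of secondary endpoints in the Protocol Summary and in section 3. The Acute Procedural Success entry in section 9 applies the same limit to "residual stenosis in the target lesion immediately post assigned treatment" and adds: "This assessment will be correlated with the ACL finding".

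Section 6.2 describes the angiographic core lab's task: "They will assess baseline lesion characteristics and post-procedural diameter stenosis". It gives no formula. No other section gives one either.

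**The concern.** The narrowest diameter divided by the native diameter is the proportion of the vessel that remains open. It falls as disease worsens, whereas stenosis rises. A ceiling of 30% on that ratio therefore selects the most obstructed vessels as successes.

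The definition also conflicts with the protocol's own use of the term. Section 1 reports that in the LACI registry stenosis was 92% at baseline "and after laser use, this decreased to" 55%, and presents this as improvement. Under the section 9 formula the same figures would mean that the laser narrowed the arteries.

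At stake are the procedural-success rate and any baseline or post-procedure stenosis summary computed from the same definition. Section 8.5 has data move from paper CRFs to an electronic database, so a CRF instruction or derived variable that copied the definition would carry the error into the analysis.

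**Working it through.** **Inputs**
- Formula as written, from section 9: narrowest lesion diameter *d* over native vessel diameter *D* at that location.
- Success limit of ≤30%, from the Protocol Summary, section 3 and section 9.
- Published stenosis values, from section 1: the LACI, CELLO and EXCITE studies.

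**Formulas**
- As written: *S_w* = (*d*/*D*) × 100.
- In the direction section 1 uses: *S* = (1 − *d*/*D*) × 100.
- Hence *S_w* = 100 − *S*.

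**What the limit means under each**
- *S* ≤ 30 requires *d*/*D* ≥ 0.70.
- *S_w* ≤ 30 requires *d*/*D* ≤ 0.30, which is *S* ≥ 70.

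**Applied to the protocol's own figures and the extremes**

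| Case | *S* (%) | *S_w* = 100 − *S* (%) | Success on *S* | Success as written |
|---|---|---|---|---|
| Total occlusion | 100 | 0 | no | yes |
| LACI, baseline | 92 | 8 | no | yes |
| EXCITE, baseline (visual, 94 patients) | 88.3 | 11.7 | no | yes |
| CELLO, baseline | 77 | 23 | no | yes |
| Upper boundary | 70 | 30 | no | yes |
| LACI, after laser | 55 | 45 | no | no |
| EXCITE, after Turbo-Elite (visual) | 49.2 | 50.8 | no | no |
| CELLO, after laser | 34.7 | 65.3 | no | no |
| Lower boundary | 30 | 70 | yes | no |
| EXCITE, final, angioplasty alone | 18.1 | 81.9 | yes | no |
| EXCITE, final, laser plus angioplasty | 11.5 | 88.5 | yes | no |
| Fully open vessel | 0 | 100 | yes | no |

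The study values are means, used here only as example lesions. All three baseline means pass as written, before treatment has had any effect, and both EXCITE final means fail.

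**Effect on the reported rate.** No lesion can meet *S* ≤ 30 and *S* ≥ 70 at once. If a proportion *p* of lesions truly succeed, the rate computed as written is at most 1 − *p*. It equals the proportion left with a stenosis of 70% or more. If every lesion were well opened, the computed success rate would be zero.

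**The case against.** The strongest reply is that nobody would score it this way. Residual stenosis plainly means narrowing that remains, section 1 uses the usual direction throughout, and the definition calls for a visual estimate, which a reader gives directly as a stenosis without computing a ratio. The procedures date from 2016–2017, so this text did not govern how operators described their results at the time. A core lab also reads the angiograms, and a 10% recorded as 90% would stand out on comparison. The reach is limited too: TLR, the primary endpoint, has no stenosis threshold, patency is judged by duplex ultrasound, and the analysis is descriptive with no hypothesis test.

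Much of this stands. The intended meaning is clear, reversed scoring is a risk of the text and not something shown to have occurred, and the damage is confined to one secondary endpoint and the stenosis summaries. Whether baseline values are affected depends on the CRF and the core lab's procedure, neither of which is in the documents.

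It does not remove the error. The core lab is given no formula, and the success definition says only that the two assessments will be correlated, not which one decides. If site values followed the written formula and core lab values the usual one, that comparison would itself be inverted. A definition should not rely on readers to correct it.

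**Conclusion.** The definition is wrong as written. It yields percent open diameter, equal to 100 minus percent stenosis, and is the only formula in the plan for a quantity that decides a named endpoint. Applied literally, it misclassifies every lesion with a true stenosis of 30% or less, or of 70% or more. Lesions strictly between those values fail either way.

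This rests on two assumptions: that the sentence is applied as it stands, and that the intended scale is the one used in section 1. It concerns procedural success, and baseline or post-procedure stenosis summaries to the extent that they use this formula. The primary endpoint of freedom from TLR at one year is not scored by it. The point must be fixed because a stated endpoint rule gives the opposite of its intended result and the correction is nearly free.

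**What to change.** Replace the Percent Stenosis entry with: percent stenosis = [1 − (minimum lumen diameter at the narrowest point of the target lesion ÷ estimated native vessel diameter at that location)] × 100. This keeps the present denominator and corrects the numerator's label, which now calls the narrowed lumen the native vessel diameter. The visual-estimate wording can stay for the site reading.

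Use the same formula in the CRF instruction, in the core lab's instructions, for baseline and post-procedure values, and in the ≤30% rule. In the same edit, state whether the site's visual reading or the core lab reading decides success.

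If values have already been recorded, check their direction before analysis: post-procedure values that run systematically higher than baseline values would indicate that the inverted form was used.

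The cost is one sentence in section 9, a matching CRF and core lab instruction, and one data check. Sample size and data collection do not change.

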The EXCITE Study used Turbo-Elite catheters to create a 2.0 mm pilot channel for Turbo Tandem in femoropopliteal in-stent restenosis (ISR) lesions. Operators could use the Turbo-Elite for multiple passes and enlarging the lumen, but Turbo Tandem was the device used to conduct maximal debulking. This study was randomized to compare ELA + PTA to PTA only with the final mean diameter stenosis by visual assessment at 11.5% vs 18.1% respectively ( $p=0.004$ ). The protocol was amended during the study to collect visual assessment data post Turbo-Elite. In 94 patients, Turbo-Elite effectively reduced baseline stenosis from  $88.3\% \pm 12.2\%$  to  $49.2\% \pm 24.8\%$  with an average mean reduction of  $39.1\% \pm 24.1\%$ . In a post hoc core lab analysis, the baseline stenosis of  $84.8\% \pm 14.7\%$  was reduced to  $58.1\% \pm 13.5\%$  with an average mean reduction of  $26.8\% \pm 14.3\%$ .

While studies have shown the decrease in stenosis with excimer laser atherectomy in a variety of lesion morphologies and arteries, there are no studies specific to Turbo Power laser atherectomy plus drug coated balloon in a variety of lesion morphologies.

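### The definitions imply that procedural success is scored on a visual estimate, and the plan does not say whether that or the planned core-lab reading governs at the 30% cut

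*Combined protocol and SAP*

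**What the plan says.** The Protocol Summary and Section 3 list procedural success, at the 30% limit, among the secondary endpoints. Neither names a reader.

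Three other places bear on how it is scored:

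- **Section 9, Acute Procedural Success.** The entry repeats the 30% limit, applied straight after treatment, and adds: "This assessment will be correlated with the ACL finding".
- **Section 9, Percent Stenosis.** The diameter at the narrowest point of the lesion is divided by the estimated native vessel diameter, "using angiographic images with visual estimate".
- **Section 6.2.** An angiographic core lab reviews procedural angiography on the 120 patients: "They will assess baseline lesion characteristics and post-procedural diameter stenosis".

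Two rules on missing data also apply. In percentages (Section 5.1), "patients with missing data will not be considered, unless otherwise specified". Section 8.2 adds: "In the event missing values are unable to be resolved, sensitivity analyses will be conducted and compared using various scenarios".

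**The concern.** Two readings of the same quantity will exist for the same patients, and the plan does not say which one decides the endpoint. The definitions point to the visual estimate, while the core-lab reading is only something to compare it with.

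Three things are at stake:

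- There is one treatment group and no comparator, so any reader bias around the 30% cut goes straight into the reported rate.
- The planned check is not specified. If it means a correlation coefficient, it cannot show whether the two readings agree at 30%.
- If the governing reading is chosen after both sets are seen, the reported rate is open to selection.

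**Working it through.** **Is there a figure to reproduce?** No. The plan gives no expected success rate, hypothesis, power or target precision for this endpoint. The check is therefore mainly a comparison of texts, followed by arithmetic on the cited data.

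**Step 1. Which reading decides success?**
- The endpoint lists name no reader.
- The Acute Procedural Success entry treats the assessment and the ACL finding as two things, since one is to be correlated with the other. ACL is not spelled out; angiographic core lab is the natural meaning given Section 6.2.
- The only definition of percent stenosis is visual.
- Section 6.2 gives the core lab the variable that the endpoint needs, but does not make it the source of the endpoint.

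A visual basis is thus an inference from two definitions. That no governing reading is stated is plain from the text.

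**Step 2. Can the two readings differ?** Section 1 gives both for one cited study, the randomized study in in-stent restenosis:

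| | Visual (94 patients) | Core lab (post hoc, number not stated) | Visual minus core lab |
|---|---|---|---|
| Baseline mean | 88.3% | 84.8% | +3.5 |
| Mean after Turbo-Elite | 49.2% | 58.1% | −8.9 |
| SD after Turbo-Elite | 24.8 | 13.5 | |
| Stated mean reduction | 39.1 | 26.8 | +12.3 |

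The stated reductions check: 88.3 − 49.2 = 39.1, and 84.8 − 58.1 = 26.7 against 26.8, which is within rounding. The two readings differ, and the sign of the difference changes between the two time points.

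**Step 3. Would a correlation coefficient show disagreement at 30%?** Let V be the visual value, C the core-lab value, and V = C + d with d constant. The correlation is then exactly 1 whatever d is. Success on the visual reading means C + d ≤ 30, that is C ≤ 30 − d.
- If d = −8.9, the visual rule is C ≤ 38.9. A patient with a core-lab value above 30 and up to 38.9 succeeds on one reading and fails on the other.
- If d = +3.5, the visual rule is C ≤ 26.5. A patient with a core-lab value above 26.5 and up to 30 is discordant the other way.

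These values of d only illustrate the mechanism. The documents do not say how many patients would lie in either band.

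**Step 4. The formula.** Narrowest diameter divided by native diameter is the fraction of lumen remaining. Percent stenosis is 1 minus that ratio. At the limit, 30% stenosis corresponds to a ratio of 1 − 0.30 = 0.70. Taken literally, a value of 30% or less under the written formula would mean stenosis of 70% or more, which cannot be what is intended for success.

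**The case against.** **The visual basis is inferred.** This stands. A reader might infer that the plan states outright that success is scored visually, perhaps by the treating operator. It does not: the words come from a general definition that names no reader. The gap remains on either view, because if the core-lab value was meant, the text does not say so.

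**The core lab may not be better.** The documents do not give its method, blinding or independence, and the visual-estimate definition does not exempt it. Preferring a separate core-lab reading is a general judgment, not something that the documents prove.

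***Correlated* may simply mean compared.** This is possible. If both readings are summarised with the descriptive statistics in Section 5.1, a constant offset would appear as a difference in means. That would still not show how many patients change category, or which reading governs.

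**Visual scoring has precedent.** One registry in Section 1 is reported that way ("From visual assessment, baseline lesion stenosis was"), and so is the randomized study's final result: "final mean diameter stenosis by visual assessment at 11.5% vs 18.1% respectively". The other registry used a core lab: "The primary effectiveness endpoint for this study was a decrease of 20% or greater after all laser by core lab assessment". Visual scoring is therefore not unusual. Reporting the visual rate as supportive keeps that comparability.

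**A size might be inferred.** A reader might apply the 8.9-point gap to final residual stenosis. With a visual mean of 11.5%, an assumed SD of 10 to 13.5 and a normal model, the core-lab mean becomes 20.4%. Success then falls from 96.8% to 83.1% (SD 10) or from 91.5% to 76.1% (SD 13.5). The documents do not support this as an estimate:
- The gap comes from an intermediate step with another catheter, at roughly 50% stenosis, and the core-lab set is post hoc and of unstated size.
- The baseline gap has the opposite sign.
- A constant offset implies equal SDs, but the cited SDs are 24.8 and 13.5.
- The model puts 12.5% to 19.7% of patients below zero stenosis.

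**Conclusion.** The point holds as a gap in the definition. Read together, the two Section 9 entries imply a visual estimate by an unnamed reader. The role of the core-lab finding is undefined, and no rule settles a conflict at 30%. A reading that is generally less open to bias is already planned on the same patients.

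The size and direction of any effect in this study are unknown. A reader might infer that visual scoring will inflate the success rate; the cited data show differences of both signs and do not support that, so no patient count should be attached to the point. The conclusion rests on taking ACL to mean the angiographic core lab and on the general view that a separate reading is less prone to bias. It concerns one secondary endpoint of a descriptive study; freedom from TLR at one year is not affected. The formula error is certain from the text and needs correcting whichever reading governs.

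**What to change.** In Section 9 (Acute Procedural Success and Percent Stenosis):

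1. State that procedural success is determined by the core-lab post-procedural diameter stenosis.
2. Report the success rate on the visual estimate as supportive.
3. Replace the statement on correlation with a 2×2 table of success by the two readings at the 30% cut, giving the number discordant in each direction.
4. Leave unreadable films out of the main percentage, in line with Section 5.1, and report how many there are. Use the visual value for them only in a sensitivity analysis under Section 8.2.
5. Correct the formula to 1 − (narrowest lumen diameter / native vessel diameter), expressed as a percentage.

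The cost is a change of wording in two definitions and one added table. Section 6.2 already plans the readings, so no new data are needed. The downside is that the reported success rate may change and a few patients with unreadable films may drop out of the main percentage.
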